2.0 OBJECTIVES AND SCIENTIFIC AIMS

1. The primary objective is to determine the feasibility of using the visual picture naming task in pediatric patients in the clinical setting. Feasibility will be defined as being able to accrue an average of 2 patients a week who successfully name and recognize sufficient numbers of pictures so that the thresholds for sedation and memory can be determined in each individual (as described in Section 11.0, Aim 1).
2. The strength of propofol amnesia (the effect of propofol on memory not related to sedation) will be estimated as a difference between thresholds for amnesia (loss of memory) and sedation (loss of verbal responsiveness)

MEMORIAL SLOAN-KETTERING CANCER CENTER IRB PROTOCOL

IRB#: 12-006A(5)

Hypothesis 1: The threshold effect for memory will occur significantly sooner, i.e. at lower drug concentrations, than the threshold effect for sedation, as illustrated in Fig 2 (the threshold for memory effect is illustrated by the light gray curves in the Figures, and for sedation by the dark curves).

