9.0 PRIMARY OUTCOMES

Several factors affect the feasibility of the proposed study design, including 1) accrual rate in the proposed 4 – 6 months study period, 2) drop-out rate (children who complete the picture naming task during infusion but fail to complete the memory task post recovery), and 3) sufficient data (e.g., few observations during the picture naming task because the child falls asleep quickly; few accurate responses during the memory task).

The accrual and dropout rates will be addressed by keeping a running tally of the number of recruited participants to monitor the recruitment numbers. Our target is to recruit at least an average of 2 out of the anticipated 4 – 6 children per week. However, it would be impractical to set a fixed recruitment target for a pilot study of this nature.

Factors associated with data sufficiency will have to be determined after the data have been collected. For example, we have to wait until the data have been collected before we can begin calculating the proposed threshold statistic (Section 14 below). The statistical computer packages may or may not be able to derive a stable estimate of the threshold measure per child. This will have to be determined after each child's data have been collected, entered, and fitted for the threshold statistics.

It is premature to anticipate a statistically reliable difference between the two threshold measures, one for the *sedative* effect threshold and the other for the *memory* effect threshold. These will have to be ascertained after the data have been collected, entered, fitted, and plotted in the manner similar to Figures 1 and 2 above. It is plausible that the threshold values are similar in some children and quite different in some other children. An important goal of this study is to examine the variability between the two threshold values among the sample of children.

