11.0 BIOSTATISTICS

Overview. This study is a pilot project to separately examine the *amnesic* and the *sedative* effects of the drug propofol. The plan is to recruit a pilot sample of 40 children who will undergo sedation as part of their clinical management and give them a memory encoding task during propofol infusion to measure the effects of *sedation*. The mere task of naming a picture will encode that picture into memory. When the anesthesia has worn off (at approximately 1 hour later), children will be given a memory recognition task to measure the *amnesic* effects of propofol. We will also recruit a total of 30 children who will not undergo sedation to serve as a control group. This brings out total number of participants to 70.

Analytic Plans for the Specific Aims:

Aim 1: The primary objective is to determine the feasibility of using the visual picture naming task in pediatric patients in the clinical setting. Feasibility will be defined as, at the conclusion of the study, 25 or more of the pilot sample of 30 (control) or 35 (propofol) per group complete the recognition memory task and yield usable parameter estimates for the psychophysics function. The probability of declaring the study design feasible is 0.51 when the true population feasibility is 0.70; and the probability of a feasible study increases to 0.92 when the true population feasibility is 0.80.

Descriptive statistics will be sought to examine study feasibility. A running tally of the number of recruited participants will be kept to monitor the recruitment numbers during the anticipated 4 – 6 months study period. Due to the complex nature of this research, many factors affect study feasibility. It would be impractical and unrealistic to set an a priori feasibility target. Rather, we will monitor several factors, including patient volume, rate of study consent, the proportion of patients who can complete the experimental tasks and the practicality of fitting the psychophysical Weibul model described below. Study feasibility will be evaluated holistically at the end of the study by the study investigators.

As for the minimally sufficient number of responses, the 10-events-per-parameter rule of thumb may apply here. (34) Although that rule was developed for logistic regression, which may or may not be too restrictive for the SAS NL MIXED procedure we intend to use to fit the threshold functions.

MEMORIAL SLOAN-KETTERING CANCER CENTER IRB PROTOCOL

IRB#: 12-006A(5)

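### Section 11 Aim 1 sets a count rule for feasibility and then withdraws it, and the 0.51/0.92 quoted for the rule fit only 25 of 35 propofol children

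*Combined protocol and SAP*

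**What the plan says.** Feasibility is the primary objective.

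- **Section 11.0, Aim 1, first paragraph.** The design is feasible if, at the end of the study, "25 or more of the pilot sample of 30 (control) or 35 (propofol) per group complete the recognition memory task" and give usable parameter estimates. One pair of probabilities of declaring feasibility follows, 0.51 at a true rate of 0.70 and 0.92 at 0.80, without saying which group it describes.
- **Section 11.0, Aim 1, second paragraph.** "It would be impractical and unrealistic to set an a priori feasibility target". Several factors will be monitored instead, and then: "Study feasibility will be evaluated holistically at the end of the study by the study investigators".
- **Section 11.0, Overview.** The propofol sample is 40 and the control sample 30, 70 in all. Aim 1 and Sample Size Considerations give 35 for propofol.
- **Section 2.0.** "Feasibility will be defined as being able to accrue an average of 2 patients a week who successfully name and recognize sufficient numbers of pictures", with a cross-reference to Section 11.0, Aim 1.
- **Section 9.0.** The target is to recruit "at least an average of 2 out of the anticipated 4 – 6 children per week", followed by the remark that "it would be impractical to set a fixed recruitment target for a pilot study of this nature".
- **Section 11.0, Sample Size Considerations.** About 10 eligible children a week, half expected to agree, and half of those expected to give data good enough for curve fitting.

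**The concern.** The first paragraph of Aim 1 is a target set in advance. The second says that no such target can sensibly be set. The factors it then lists include the proportion completing the tasks and the practicality of fitting the model. Those are the quantities that the count rule uses, now without a cut-off.

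A reader who sees 0.51 and 0.92 will take them as the operating characteristics of the primary decision. If the decision is a judgement, no such probability can be calculated, and the risk of calling a poorly performing design feasible is not controlled. Even if the rule is applied, one pair of probabilities cannot serve two groups that share the cut-off of 25 but differ in size.

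**Working it through.** **Inputs.** Cut-off 25; n = 30 (control) and 35 (propofol), from Aim 1; n = 40 (propofol), from the Overview; true rates 0.70 and 0.80, from Aim 1; usability 0.50, from Sample Size Considerations.

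**Formula.** With X usable children out of n, independent with common rate p: P(X ≥ 25) = Σ C(n,k) p^k (1−p)^(n−k), summed over k = 25 to n.

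**Reproducing the plan's figures.** For n = 35 the tail is 0.510 at p = 0.70 and 0.925 at p = 0.80, which agrees with the stated 0.51 and 0.92. A search over n from 20 to 74 and cut-offs from 10 to n found no other pair that matches both.

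**The same cut-off with each denominator in the documents.**

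| Rule | Cut-off as a proportion | p = 0.50 | p = 0.70 | p = 0.80 |
|---|---|---|---|---|
| Propofol, 25 of 35 | 71% | 0.008 | 0.510 | 0.925 |
| Control, 25 of 30 | 83% | 0.0002 | 0.077 | 0.428 |
| Propofol, 25 of 40 | 62.5% | 0.077 | 0.885 | 0.997 |

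**If the groups are combined (30 and 35).** The text does not say whether one or both must pass. Assuming independent groups with the same true rate:

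- Both must pass: 0.077 × 0.510 = 0.039 at 0.70, and 0.428 × 0.925 = 0.396 at 0.80.
- Either suffices: 1 − (1 − 0.077)(1 − 0.510), which is 0.547 from unrounded values, at 0.70; likewise 0.957 at 0.80.

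**A result on which the two paragraphs can part.** 20 of 35 usable is 57%, exact (Clopper-Pearson) 95% CI 39% to 74%. It fails the first paragraph. Nothing in the second prevents a conclusion of feasible.

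**The plan's own usability assumption.** Sample Size Considerations describes the 35 as accrued and expects half of consenting children to give data fit for curve fitting. On that reading P(X ≥ 25) with n = 35 and p = 0.50 is 0.008, so the plan's assumption predicts that its rule will fail. If the 35 are instead children who already have usable data, the rule is met almost by construction. The documents do not settle which is meant. The 50% is stated for children having anesthesia, so it does not carry over to the controls.

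**Accrual measures.** Section 2.0 counts children with usable data per week; Section 9.0 counts children recruited per week. On the plan's figures, 10 × 0.5 = 5 consent and 5 × 0.5 = 2.5 are usable each week, so both are expected to be met.

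**The case against.** The best defence is that this is a small, non-randomised pilot, where judgement about feasibility is legitimate. The plan states no order of precedence between the two paragraphs, and the holistic review could be read as interpreting the count. Completion proportions will be described, so readers should see a result such as 20 of 35. What stands is that judgement is an acceptable design if it is labelled as such. What does not stand is that the count can be merely interpreted when the next paragraph says that no advance target is realistic.

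Some stronger readings are tempting but not supported:

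- **Sections 2, 9 and 11 give three rival definitions.** Section 2.0 refers to Aim 1, and Section 9.0 lists accrual as one of three factors beside drop-out and data sufficiency. The accrual figures can be components of one endpoint. The wording differs, but the firm contradiction is inside Aim 1.
- **The plan would meet Section 9.0 and fail Section 2.0.** Two recruited a week at 50% usability does give one usable child. That pairs Section 9.0's minimum with an assumption made for about five consenting children a week. It shows that the measures differ, not that the plan expects them to conflict.
- **The true chance of success is 0.04 or 0.40.** Those figures need both groups to pass and equal usability in sedated and unsedated children. The plan states neither.
- **The 0.51 and 0.92 are miscalculated.** They are right for 25 of 35.

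**Conclusion.** The point holds. On the primary objective, Aim 1 sets a decision rule with operating characteristics and then leaves the decision to a judgement that the rule does not bind, so 0.51 and 0.92 do not describe the decision. The pair is also valid for only one of the two groups that the rule names: 0.510 and 0.925 for propofol at 35, against 0.077 and 0.428 for controls. With the Overview's 40 propofol children it becomes 0.885 and 0.997.

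These figures assume independent children with a common rate within each group. The 0.008 further assumes that 35 counts children accrued and that the 50% applies to them. The differing accrual wording in Sections 2.0 and 9.0 is a secondary matter of consistency.

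**What to change.** State one binding count rule in Aim 1:

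- Say whether it applies to each group separately or to both jointly.
- Reconcile the propofol denominator (35 or 40), and say whether it counts children accrued or children who already have usable data.
- Fix in advance what makes an estimate usable. Sections 9.0 and 11.0 leave this open, and a count of an undefined event still leaves discretion.
- Report each group's usable proportion with an exact 95% CI.
- Give the probabilities for each group, and jointly if both must pass. Include 50% usability for propofol, and restate the cut-off or the assumption if a pass probability of 0.008 is not intended.

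Delete the sentence ruling out an advance target, and limit the holistic review to descriptive interpretation that cannot overturn the rule. Word Sections 2.0 and 9.0 alike, with two usable children a week as the secondary accrual criterion.

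If judgement is truly intended, remove the count rule and the 0.51/0.92 instead, and describe feasibility as estimation only.

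The count-rule option costs more than editing, because the cut-off, denominator, group logic and usability criterion each need a decision. The investigators lose discretion to call a failed count feasible, and the stated probabilities will look less favourable, most of all for the controls.

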4.2 Intervention

During induction of sedation, or in the case of no sedation, before the therapeutic procedure, children will be encouraged to name the items shown in pictures displayed, one every 5 seconds, as drug concentration is increasing. Naming pictures will ensure that items are being attended to and memory systems are engaged. The child's response will be used to assess the degree of sedation present (response present / response absent). After recovery from sedation, or after a similar time period after the therapeutic procedure

MEMORIAL SLOAN-KETTERING CANCER CENTER IRB PROTOCOL

IRB#: 12-006A(5)

(approximately 40 min) for children in the control group memory for the previously presented pictures will be tested using a yes/no response. The recognition testing set will contain both previously seen and novel items.

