7.0 ASSESSMENT/EVALUATION PLAN

The recognition memory task will consist of simple line drawings selected from a larger stimulus data base (<http://crl.ucsd.edu/experiments/ipnp/method/getpics/getpics.html>) based on their age appropriateness and identifiability by children in the target age range. Stimulus items are presented by means of a bound stimulus book with one black and white line drawing presented on each page. A brief test will be performed to familiarize the child with performing the picture naming task, using different pictures from those that will be shown in the study. If the child is not able to cooperate sufficiently with the test task, then he/she will be withdrawn from the study and propofol will then be administered as per normal clinical practice for their procedure. If sedation will be needed, propofol infusion will be started at a rate to deliver 3mg/kg over a 10 minute period. During this learning phase of the study, pictures will be presented to the participant and the participant will be asked to name each object pictured with accuracy and non responses will be recorded by the examiner. If sedation is being given, the drug infusion rate will be adjusted according to clinical observation (e.g. excessive sedation/no drug effect apparent) so that the patient will be appropriately sedated for the planned procedure by the end of the 10 minute infusion period. After conclusion of the initial infusion, propofol will be administered as per usual practice. Following the procedure after awakening in the PACU, when no apparent sedation is

Amended: 6/10/13

MEMORIAL SLOAN-KETTERING CANCER CENTER IRB PROTOCOL

IRB#: 12-006A(5)

present, or after a similar time period, if no sedation was used, the picture recognition phase of the study will be performed. Patients will again be presented the original pictures with an equal number of pictures not seen during the infusion phase. The order of pictures in the learning (propofol infusion) and recognition phases(PACU) will be the same for every patient. The child will indicate whether the picture was seen before (yes/no). The study is complete. The child will be discharged form the PACU as per standard clinical criteria."

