Aim 2. Illustrative Examples. Aim 2 involves the calculation of a “sedation threshold” and a “memory threshold” for each child. Figures 1, and 2 provide illustrative examples on how the separate sedative and amnesic effects will be estimated statistically. An example is provided below to explain the procedures and the analytic plan.

1. “Sedation threshold”: During the 10-minute infusion of propofol, children will be presented with pictures at 5-second intervals and asked to name the picture. They will be asked to name each picture (e.g., cat, tree, pencil, etc.). A valid response is naming of the picture within 5 seconds, either correctly or incorrectly. The important response measure is whether the child is awake enough to perform the naming task. Though the picture list is a validated set of stimuli, as described in Section 7.0, some stimuli may end up being too difficult to name for children of this age group. Thus no response due to sedation may be confounded by no response due to an inappropriately difficult stimulus. Responses from the control group of children will be used to eliminate problematic stimuli which reach a given criterion of no response at both sites.

In Figures 1 and 2, the dark circles with a value of 1 on the y-axis represent that the participant is making valid responses. The dark circles with a value of 0 on the y-axis represent lack of a valid response because the participant is sedated to the point of impaired response performance as propofol concentration continues to increase. As the child gets sedated and becomes gradually sleepier as the infusion continues, he/she is less likely to make a valid response (thus the increased frequency of dark circles at the bottom of the Figures as image number increases). The dark line in Figure 1 represents the estimated sedative effects over time.

There is a vast literature in psychophysics on modeling the shapes of these curves. Since the seminal paper by Quick (1974; *Kybernetik*, 16: 65-67; PMID: 4453110), the model below has been used extensively in modeling various psychophysical functions. We will use an asymmetric Weibull cumulative density function $F(x)$ to model the overall probability of a valid response $G(x)$ over time x :

$$\begin{aligned} G(x) &= 0.5 + 0.5 \cdot F(x) \\ &= 0.5 + 0.5 \left[1 - e^{-(\alpha \cdot x)^\beta} \right], \end{aligned}$$

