where $\alpha > 0$ and $\beta > 0$ are the scale and shape parameters, respectively, and $x \geq 0$. (35) The constant of 0.5 assumes a 50-50 chance of a random response in a psychophysical task. Conventionally, the median of $F(x)$ is called the “threshold” of the underlying psychometric function (the value of x for which $F(x) = 0.5$). Because of the assumed 0.50 constant in $G(x)$, and the 0.5 times the median of the Weibull, the threshold estimate is the x value of an overall 75% response probability given the Weibull parameters. The threshold of a psychometric function generally represents the strength of stimulus that elicits a sensation or a noticeable difference. In this case the sedation threshold represents the time value of x when sedation is actuated. We will estimate one sedation curve and its corresponding threshold for each child.

MEMORIAL SLOAN-KETTERING CANCER CENTER IRB PROTOCOL

IRB#: 12-006A(5)

2. "Memory threshold": When the anesthesia has worn off at approximately 1 hour later, the child will be presented with another list of 120 pictures with half having been presented during the initial infusion of propofol. At the presentation of each picture, the child will be asked whether or not he/she remembers having seen it previously. Each response will be coded as correct (true positives and true negatives) or incorrect (false positives and false negatives). A curve may be fitted to the memory recognition data to estimate the average memory decay function for each child. In Figure 1 and 2 this is represented as the light gray curve, which can be modeled as $1 - G(x)$ above. Similarly, a threshold represents the time value (picture number) when memory fades below threshold.

The *sedation* threshold in Figure 1 is at image 25 (250 seconds), while the *memory* threshold is at approximately image 28 (280 seconds). This 30-second / 3 picture difference is taken to represent that sedation occurs concurrently with memory decay. Alternatively, in Figure 2, the *sedation* threshold is at image 58 (580 seconds) while the *memory* threshold is approximately at image 40 (400 seconds). This larger difference of 180 seconds / 18 pictures is a measure of how much sooner amnesia occurred in this instance than sedation. In this latter case, a measurable amnesic effect of 180 seconds can be inferred from the two threshold values.

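### The printed threshold curve G(x) can only rise from 0.5 to 1, while the naming it models falls, so the formula yields no meaningful sedation threshold; its mirror image for memory is capped at 0.5

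*Combined protocol and SAP*

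**What the plan says.** Section 11.0, Aim 2, defines G(x) = 0.5 + 0.5[1 - exp(-(αx)^β)] with α > 0, β > 0 and x ≥ 0. It commits to this curve "to model the overall probability of a valid response $G(x)$ over time x". The 0.5 is explained as a 50-50 guess rate. The threshold is the point where F(x) = 0.5, which the section equates with a 75% response probability.

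The same subsection describes the naming data. A valid response is coded 1 and its absence 0, and as the infusion continues the child becomes sleepier, so that "he/she is less likely to make a valid response".

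For memory, the section says that the recognition curve can be modelled as 1 - G(x). The wording there is permissive, but the paragraph on calculating the thresholds then plans G(x) functions for both curves in each child. Aim 1 counts children who complete the recognition task and give usable parameter estimates: 25 or more of 30 controls and of 35 propofol children.

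**The concern.** The curve and the data run in opposite directions. No permitted α and β make G fall or drop below 0.5. The guess rate also has no basis for open naming: a sedated child does not guess between two options but says nothing. For memory, 1 - G(x) does fall, but it starts at 0.5, so it cannot describe a child who recognises most pictures shown before the drug acts.

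Both per-child thresholds, the difference tested under Hypothesis 1 and the Aim 1 count depend on this formula. Section 9.0 already expects that software may fail to give a stable threshold for some children. With the printed equation such a failure would come from the equation but could be read as a failure of the task.

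**Working it through.** **Inputs.** The formula and constraints are from Section 11.0, Aim 2. True sedation thresholds of 250 and 580 s and a true memory threshold of 400 s are the section's own Figure 1 and Figure 2 examples; 450 s is an assumed value in between. Weibull shapes (4, 6 and 12 for naming, 5 for memory), recognition before drug effect (U) and false-positive rates (FA) are assumptions, since the documents give none.

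On picture count, the recognition test is "another list of 120 pictures with half having been presented during the initial infusion of propofol", which implies 60 shown, whereas "children will be presented with pictures at 5-second intervals" over 10 minutes implies 600/5 = 120. Picture numbers below are out of 60. With 120 the thresholds in seconds agree closely wherever one exists, and the conclusions are the same.

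**Step 1: the plan's own figure.** At the Weibull median F = 0.5, so G = 0.5 + 0.5 × 0.5 = 0.75. The stated 75% is reproduced.

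**Step 2: range.** G(0) = 0.5 + 0.5 × 0 = 0.50, and G tends to 0.5 + 0.5 × 1 = 1.00. So 1 - G runs from 0.50, through 0.25 at its threshold, to 0.

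**Step 3: G fitted to falling naming data.** Expected naming is p(x) = exp[-ln 2 (x/m)^shape], with m the true threshold. The fit maximises Σ[p ln G + (1 - p) ln(1 - G)]. For a falling p, the best non-decreasing curve with a floor of 0.5 is flat at max(0.5, mean p).

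| True threshold | Mean naming | Best flat level | Threshold from G as printed |
|---|---|---|---|
| 250 s (picture 25) | 0.41 | 0.50 | runs to the upper search limit |
| 450 s (picture 45) | 0.73 | 0.73 | beyond the list at every shape bound tried |
| 580 s (picture 58) | 0.93 | 0.93 | picture 16.0, 4.8, 1.1 or 0.0009 at shape bounds 1, 0.5, 0.3 and 0.1 |

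No G fit beat the flat line, and a lower bound moved the fit closer to it. A falling curve, 1 - F(x), fitted to the same expected data returns 250, 450 and 580 s exactly. That is expected, since the data came from that family, but it locates the failure in the printed form rather than in the data.

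**Step 4: 1 - G fitted to recognition.** Expected recognition of old pictures is FA + (U - FA)(1 - F(x)), with U = 0.95 and a true threshold of 400 s.

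| FA | Recognition at the true threshold, FA + (U - FA)/2 | Threshold from 1 - G |
|---|---|---|
| 0.05 | 0.05 + 0.45 = 0.50 | about 492 s |
| 0.10 | 0.10 + 0.425 = 0.525 | about 512 s |
| 0.30 | 0.30 + 0.325 = 0.625 | about 595 s |
| 0.50 | 0.50 + 0.225 = 0.725 | none |

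The fitted curve places its threshold at 0.25, far below recognition at the true one. Over U from 0.85 to 1.0, shapes 3 to 8 and FA from 0 to 0.50, the estimate is late in all 45 settings (earliest 439 s) and beyond the list in 12. With FA = 0 the lateness shrinks as U falls: U = 0.6 gives 427 s and U = 0.5 gives exactly 400 s.

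**Step 5: is the intended reversal obvious?** Two natural repairs disagree. Reversing G but keeping the 0.5 floor gives about 194, 380 and 533 s for true 250, 450 and 580 s. Fitting naming by 1 - G gives picture 28 to 31 for a true 25 and no finite threshold for a true 58.

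**The case against.** The strongest reply is that the intent is plain. Section 3.0 and Aim 2 both describe falling curves, and the team has fitted volunteer data before, so the equation may be a slip in transcription. Section 9.0 has the fits plotted like Figures 1 and 2, where a flat line would be noticed, and the raw data could be refitted. This is a pilot whose feasibility is judged holistically, and Section 9.0 calls it premature to expect a reliable threshold difference. All of that stands, and it limits the harm to what happens if the formula is coded literally. It does not supply a curve: the obvious reversals give different thresholds, and a choice made after seeing flat fits is made with the data in view. The safeguard that "Responses from the control group of children will be used to eliminate problematic stimuli" may raise naming before sedation but does not turn the curve round.

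Three stronger readings are tempting and are not supported.

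- That the memory threshold is late or absent whatever the data. It depends on recognition before drug effect exceeding 0.5 or on false positives; recognition running from 0.5 to 0 is recovered without bias.
- That the Figure 2 difference of 180 s would become 580 - 492 = 88, 580 - 512 = 68 or 580 - 595 = -15 s. This presupposes a correct sedation threshold, which the printed formula does not deliver. It shows only the direction of the memory error, which is against Hypothesis 1.
- That F(x) = 0.5 is the 50% effect of Section 3.0. The figures are not available to confirm it. If the horizontal line there marks 50% response probability, the quantities differ: with U = 0.95, FA = 0.30 and shape 5, solving 0.30 + 0.65(1 - F) = 0.50 gives x = 400 × [-ln(0.20/0.65)/ln 2]^(1/5) ≈ 445 s, not 400 s.

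**Conclusion.** The concern holds and should be corrected before any curve is fitted. The sedation part is algebra on committed text: G cannot describe falling naming for any permitted parameters. The fitted threshold is then at a search limit, past the list or chosen by a software bound; the particular values rest on the assumed shapes. The memory part is certain as to the ceiling of 0.5 and conditional as to its effect. If recognition before drug effect is above 0.5, as the design needs, or false positives occur, the threshold is late or absent: about 92 to 195 s late (492 - 400 to 595 - 400) at U = 0.95, shape 5 and FA of 0.05 to 0.30. Aim 2, Hypothesis 1 and the Aim 1 count all depend on the formula. Data collection does not, and nothing already recorded would be lost.

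**What to change.** Replace the formula in Section 11.0, Aim 2, and the reference to G(x) functions in the paragraph on calculating the thresholds, with two falling curves, each with its own α and β:

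- Sedation: P(valid naming at x) = L(1 - F(x)), with L the naming level before sedation and no 0.5 constant. L = 1 is adequate only if naming is essentially complete before sedation.
- Memory, old pictures only: P(yes at x) = FA + (U - FA)(1 - F(x)), with FA the child's yes-rate on novel pictures and U recognition before drug effect.

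Keep the threshold at F(x) = 0.5, state that it means half of the drug effect rather than 50% response probability, and delete the 75% and 1 - G(x) statements. The team should fix in advance whether L and U are per child or common, what the search bounds are, and how a child with no threshold inside the list counts in Aim 1 and in the one-sample t-test. Undrugged controls with flat performance have no threshold to find, so usable in that group should not require one.

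The cost is wording and a few lines of code. The downside is up to one extra parameter per curve: under the 10-events remark in Aim 1, 3 × 10 = 30 events rather than 2 × 10 = 20. With 60 pictures and L = 1, the rarer naming outcome is expected about 24, 16 and 4 times at 250, 450 and 580 s. Some children with late sedation will still have no threshold inside the list. In simulation under assumed recognition and false-positive rates, about 75% (60 pictures) to 84% (120 pictures) had both thresholds inside it at 580 and 400 s.
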